8.6 Multi-centre studies

This is a multicenter study, with sites enrolling subjects in the USA, UK and Spain with each site enrolling 1 -2 subjects. Efficacy data collected from all study centers will be pooled for data analysis.

8.7 Multiple testing

There will be no adjustments for multiple comparisons in this proof of concept study.

8.8 Baseline values

Baseline is considered the value collected at the Day 1 Week 1 visit. If Day 1 Week 1 value is missing, the Screening value will be used as baseline. If neither a Day 1 Week 1 or Screening value

is available, then the baseline value will be imputed according to the MI and LOCF methods described in Section 8.4.

Some analyses will be also presented comparing pre-dose and post-dose effects. Unless otherwise specified, post-dose and pre-dose comparisons will be done using data from the same study day.

8.9 Reporting conventions

8.9.1 General reporting conventions

All tables, figures and data listings will be presented in landscape orientation. Legends will be used for all figures with more than one variable or item displayed. Figure lines should be wide enough to see the line after being copied.

All tables, figures, and listings, (TFLs) will have the name of the relevant SAS program (output name), the author, and a run time stamp on the bottom of each output.

Titles should contain the following information:

- Output number.
- Description of the data that is being summarized.
- Type of analysis performed, covariates used (if applicable).
- Analysis set.

8.9.2 Statistical summary conventions

For tables, sample sizes for each population will be presented as totals in the column header (N=xx), where appropriate. Sample sizes shown with summary statistics are the number (n) of subjects with non-missing values at a visit.

Summaries for categorical variables will include all categories (even if some categories are empty). All summaries for continuous variables will include: N, mean, and SD. Other summaries (e.g. SE, median, quartiles, range, 95% intervals, CV or %CV) will be used as appropriate. All percentages should be rounded and reported to a single decimal place (xx.x%). If percentages are reported as integers, percentages greater than 0% but <1% will be reported as <1%, whereas percentages greater than 99% but <100% will be reported as >99%. A percentage of 100% will be reported as 100%. No value of 0% should be reported. Any computation of percent that results in 0% is to be reported as a blank. P-values will be reported with up to three decimal places with a leading zero (0.001). P-values <0.001 will be reported as <0.001. Summaries for continuous variables will be presented with the same number of decimal places as originally provided in the CRF.

9. STATISTICAL ANALYSIS

9.1 Baseline and other relevant data

9.1.1 Subject disposition

The number of subjects who were enrolled, completed each visit, and discontinued, and reasons for discontinuation will be summarized (Shell T - 1).

9.1.2 Protocol deviations

Deviations from the Clinical Study Protocol will be collected by the monitors, including deviations of inclusion/exclusion criteria will be assessed and categorized by the Sponsor. The number of subjects with protocol deviations (any, major, minor and by deviation) will be summarized descriptively (Shell T - 2). All the collected information regarding protocol deviations will be listed.

9.1.3 Analysis sets

The number of subjects included and excluded in each analysis set will be described (Shell T - 3). Subjects excluded from any analysis set will be listed including: analysis set from which it is excluded, and the reasons for exclusion (Shell T - 3).

9.1.4 Demographics and other baseline characteristics

The following variables will be summarized (Shell T - 4):

Demographics: Age, Sex, Race, Ethnicity, Weight, Height, and BMI as recorded at the Screening visit. BMI will be presented as a continuous variable and for the following categories: “<20”, “20-25”, and “>25”.

Disease characteristics: Intense Pain (Yes/No), VAS score, Firm calcified (Yes/No/NA), cutaneous lesions (Yes/No), Skin biopsy (Yes/No/Scheduled/Not done), Results of the biopsy (Yes/No/Not applicable/To be redone).

History of drug and alcohol abuse: Alcohol Consumption (Yes/No), total units of alcohol consumed weekly, and Drug Consumption (Yes/No), recorded in the Medical History CRF section.

9.1.5 Medical History

The following tables will be created (Shell T - 4):

General: contains a Yes/No variable for each domain: Hemodialysis, Heart, Vascular System, Parathyroid, Diabetes, Kidney Diseases, Fractures, Liver Diseases, Other Diseases. For each domain we will consider as “Yes” if the subject has any non-negative (i.e. excluding No, UNK and missings) answer for at least one question related with the domain and “No” in the other cases.

The data related with each domain will be summarized and listed. The information summarized will be presented only for the subjects who has a “Yes” in the General table, but all subjects’ information will be listed.

For each domain, the following variables will be summarized:

Hemodialysis: Ca-Conc, URR and Kt/V.

Heart: NYHA Stage, CHD, Heart failure, LVEF, MI, Bypass Surgery and PTCA.

Vascular System: PAD and Stage Fontaine.

Parathyroid: PTX, and Method.

Diabetes: Diabetes, Type, and Insulin dependent.

Kidney Disease: Renal insufficiency, CKD, Origin, Renal hypert., Metab. Acid., Osteopathy, Anemia, and 2nd HPT.

Additional Diseases, Fractures: Occurrence by each Location.

Additional Diseases, Liver Diseases: Occurrence by each Condition.

Additional Diseases, Other: Primary HPT, Malignant, and Rheumatic.

9.1.6 Prior and Concomitant medications

Prior and concomitant medications will be tabulated and listed for the safety analysis set.

Prior medications are defined as those taken from 6 months prior to Screening until the time of the first treatment dose administration. Concomitant medications are defined as those taken at the time of or after the first treatment dose administration.

Prior and concomitant medication will be coded according to the World Health Organization's Drug Dictionary (WHO-DDE) and the Anatomical Therapeutic Chemical (ATC) classification system.

Prior and concomitant medications will be summarized separately by ATC Name and Preferred Term indicating the number of subjects and percentage (Shell T - 5). When calculating the use of prior/concomitant medications, each subject will only be counted once and any repetitions of medications will be ignored; the denominator will be the total population size.

A separate table will be presented for Pain Medications. Pain medication will be defined from the list of Concomitant Medications, according to coding specified by the study sponsor which should be merged with the Concomitant Medications dataset by Drug Record Number and Sequence 1.

9.1.7 Treatment exposure and compliance

The extent of exposure to SNF472 will be characterised according to the number of subjects exposed, the duration of exposure, and the dose to which they were exposed.

The following data will be summarized descriptively for the total treatment period and by week (Shell T-6):

- **Treatment duration (days)** defined as the total number of days between the first and the last infusion dates (inclusive).

-
- **Treatment exposure (infusions)** defined as the number of infusions with the study drug of at least 1 hour that were administered to a subject.
 - **Compliance (%)** defined as the total number of infusions administered to a subject divided by the total number of planned infusions, i.e, 3 administrations x 12 weeks of treatment = 36.
 - **Dose (mg)** presented as a categorical variable indicating the number and percentage of subjects presented on the different planned dose levels (400, 450, 700, and 900 mg).
 - **Total dose (mg) (an estimation of the total dose)**
 - **Dialysis duration (minutes)** defined as the time in minutes registered between the start of the dialysis start and it end.
 - **Infusion duration (minutes)** defined as the time in minutes registered between the start of the infusion and its end.
 - **Number of infusions with any interruptions** counting the number of infusions per subject where the question "Infusion interruptions" is Yes.
 - **Ca in Dialysate Bath** presented as a categorical variable.

9.2 Efficacy Analysis

9.2.1 Primary endpoint

The primary endpoint is the absolute change in BWAT total score between baseline (Week 1) and Week 12 for the primary lesion (the largest one).

Absolute change from baseline will be calculated as differences in the total score from Week 1 to Week 12. Descriptive statistics will be presented. Differences between the two visits will be analyzed using a Paired Student's T-Test. (Shell T-7)

Missing imputation will be done on the item level. For the imputation of baseline missing item scores FOCB will be used for LOCF imputation method if any subsequence item score is available, else the score will be imputed by 3. For the multiple imputation method the baseline values will be imputed by 3. The main analysis will be done using Multiple Imputation, and supported by the different sensitivity analysis as specified in Section 8.4. A forest plot summarizing these results will be produced presenting the estimated change from Week 1 to Week 12 and its 95% confidence interval for the different imputation methods (Shell F - 1).

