6.6 Study methods

6.6.1 Bates-Jensen Wound Assessment Tool (BWAT)

The Bates-Jensen Wound Assessment Tool (BWAT) score is collected through a questionnaire of 13 items, which are evaluated individually with a score of 1 to 5. BWAT is summarized by a total score which is calculated by adding up the scores of all individual items. Therefore, the total score ranges from 13 to 65 and can be only calculated if all items are answered. However, for the purpose of this analysis missing items were imputed as described in Section 8.4. Note that the BWAT contains two extra variables to indicate the location and shape of the lesion that are not used for the calculation of the total score.

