8.4 Missing data

This section provides a general description about methods used to impute missing data. Specific details for imputed variables will be given in Section 9.2.

Missing imputation will be only applied for the primary and key secondary endpoints, i.e. BWAT, VAS and Wound QoL. The main analysis will be based on Multiple Imputation (MI). Sensitivity analyses will be conducted to assess the robustness of the results with regards to handling of missing data. The following methods will be applied: Last Observation Carried Forward (LOCF), and Observed Cases (OC) (Molenberghs & Kenward, 2007).

Multiple Imputation

Multiple imputation was selected as the method for imputing missing data as the natural progression of calciphylaxis skin lesions under standard of care treatment varies considerably [Nigwekar et al, 2013]. Rather than making assumptions under the LOCF method that may either be too optimistic or conservative relative to the natural progression of skin lesions under standard

of care treatment, multiple imputation uses all available data for a given variable to impute for missing data. Missing data will be imputed 100 times to generate 100 complete data sets, using the MI SAS procedure (using *Markov Chain Monte Carlo (MCMC)* for continuous variables or the *Fully Conditional Specification (FCS) Discriminant* analysis for categorical variables). The absolute change from baseline at Week 12 will be then derived from observed and imputed data at this time point. The 100 complete data sets will be then analyzed using a paired t-test, and the MIANALYZE procedure will be used to generate valid statistical inferences by combining results from the 100 analyses using Rubin's formulae.

The number of imputations (100) will be informally verified by replicating sets of 100 imputations and checking whether the combined results are stable. If not stable, the number of imputations will be increased and informally checked as above, and thus until stable estimates are obtained.

The imputation model will include:

- The endpoint values from all non-missing scheduled weeks.
- The endpoint values from other items within the same scale, if applicable.

LOCF

This analysis imputes the last measured value of the endpoint to all subsequent evaluations. In case of missing data at baseline, the missing value will be imputed using the first available visit, i.e., First Observation Carried Backward, FOCB.

Observed Cases

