The analysis under this scenario will be conducted without any missing data imputation.

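### The main multiple-imputation analysis replaces a missing Week 1 BWAT item by 3 even when later scores of that item exist, which can shift the primary result either way with no added uncertainty

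*SAP*

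**What the plan says.** SAP 9.2.1 imputes BWAT item by item and gives two rules for a missing Week 1 item.

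- **LOCF (supportive):** the first later score is carried backward (FOCB) "if any subsequence item score is available, else the score will be imputed by 3".
- **Multiple imputation (main analysis):** "For the multiple imputation method the baseline values will be imputed by 3". No condition is attached.

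The results by imputation method are to be shown together in a forest plot.

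Other sections bear on this:

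- SAP 6.6.1 says the total "can be only calculated if all items are answered", and adds: "However, for the purpose of this analysis missing items were imputed as described in Section 8.4".
- SAP 8.4 prefers multiple imputation because "multiple imputation uses all available data for a given variable to impute for missing data". Its model takes in every available scheduled week and the other items of the scale. It also says: "Specific details for imputed variables will be given in Section 9.2". On Observed Cases it says: "The analysis under this scenario will be conducted without any missing data imputation".
- SAP 8.8 replaces a missing Week 1 value by the Screening value; if that is missing too, "then the baseline value will be imputed according to the MI and LOCF methods described in Section 8.4".
- SAP 9.2.2.1 and the visit schedule place the first BWAT at Week 1, so there is no Screening score.
- Protocol 7.5.2 (also 4.2.1 and 7.5) makes the parts of BWAT that need probing or depth measurement optional.
- SAP 9.7.1 applies the 9.2.1 rule to the BWAT subgroup analysis.

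**The concern.** SAP 6.6.1 and 8.8 point to 8.4, but 8.4 hands the details to 9.2. The constant in 9.2.1 is therefore what would be programmed. The main analysis then discards scores that the sensitivity analysis uses, against the reason 8.4 gives for choosing multiple imputation.

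A fixed value at baseline goes straight into the change score. It is the same in all 100 data sets, so Rubin's rules see no between-imputation variance from it. With a single arm, no comparison cancels the error. Since some BWAT items are optional, gaps at Week 1 are foreseeable. In a study of about 15 patients, the rule could create an apparent improvement or hide a real one, and its result would stand as the primary one.

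**Working it through.** **Plan's own figure.** The only design figure is 15 subjects for 60% against 25% with 80% power (SAP 6.4). With success at 8 or more responders of 15, the exact binomial gives one-sided alpha 0.0173 and power 0.787, so 15 is reproduced. Only N = 15 is used below.

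**Step 1: shift per patient.** Let b be the true Week 1 item score and w the Week 12 score, both on 1 to 5 (SAP 6.6.1). The true change is w - b and the analysed change is w - 3, so the error is (w - 3) - (w - b) = b - 3. It runs from -2 (b = 1) to +2 (b = 5). Lower is better on BWAT, so b below 3 exaggerates improvement and b above 3 understates it.

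**Step 2: shift of the mean.** With k items missing in each of m patients, the shift is k × m × (mean b - 3) / 15.

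- k = 1, m = 1, b one point from 3: 1 × 1 × 1 / 15 = 0.07.
- k = 2, m = 3, b one point from 3: 2 × 3 × 1 / 15 = 0.40.
- k = 2, m = 8, b one point from 3: 2 × 8 × 1 / 15 = 1.07.
- k = 2, m = 8, b two points from 3: 2 × 8 × 2 / 15 = 2.13.

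**Step 3: effect on the test when nothing changes.** The documents give no missingness rates, item means or SD of change, so these are assumptions. The simulation used n = 15, two items (rounded normal, SD 0.9, kept within 1 to 5), seven visits and between-visit correlation 0.7. The items were missing at Week 1 only. There were 2,000 runs with 20 imputations and Rubin pooling. The SD of total change was 3 and the nominal level 5%. Each pair is for true item mean 2 / 4.

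| Patients affected | Shift of mean change | Rejection rate, constant 3 |
|---|---|---|
| 1 | -0.13 / +0.13 | 0.049 / 0.047 |
| 3 | -0.38 / +0.38 | 0.059 / 0.057 |
| 5 | -0.63 / +0.63 | 0.110 / 0.106 |
| 8 | -1.02 / +1.02 | 0.209 / 0.195 |

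From three patients upward, the shifts are slightly below Step 2 because the 1 to 5 limits pull the realised item means towards 3. With SD 6, the rejection rates are 0.056 / 0.060 (3 patients) and 0.090 / 0.095 (8 patients). Drawing the item by discriminant analysis from its Week 2 score gave absolute bias of 0.02 or less and rejection of 0.033 to 0.054 in these cases.

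**Step 4: effect when there is a real improvement.** Both items improve from 4 to 3, the total change is -1.9 and the SD is 3.

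| Patients affected | Change reported with constant 3 | Power, complete data | Power, constant 3 | Power, discriminant draw |
|---|---|---|---|---|
| 3 | -1.9 + 0.38 = about -1.5 | 0.647 | 0.434 | 0.625 |
| 8 | -1.9 + 1.02 = about -0.9 | 0.632 | 0.161 | 0.564 |

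**Step 5: a second simulation with all 13 items.** Two baseline items were missing in 7 of 15 patients.

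- Baseline item mean 4: complete data -12.50, constant -11.58 (shift +0.92), imputation from the Week 2 score -12.49.
- Baseline item mean 2: complete data -5.27, constant -6.16 (shift -0.89), imputation from the Week 2 score -5.29.

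The standard error was 1.065 with the constant against 1.093 with imputation (mean 4), and 1.067 against 1.106 (mean 2), so about 3% to 4% too low. The between-imputation variance from the baseline items was about 0.03 with imputation and exactly 0 with the constant.

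**The case against.** The harm needs a specific pattern: the item is unscored at Week 1 and scored at Week 12. The only documentary reason to expect gaps is that probing and depth items are optional, and a physician who declines to probe at Week 1 may never probe that wound. Such items get 3 under any workable rule, and no inflation is claimed for them. With one to three patients affected, the shift is 0.13 to 0.38 point on a 13 to 65 scale and the test stays near nominal. The 20% figure needs 8 of 15 patients.

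The power loss also depends on the effect. With the same 0.38 bias, power falls only from 95% to 88% for a change of -3 (SD 3), from 99.8% to 99.1% for -4 (SD 3), and from 85% to 79% for -5 (SD 6). LOCF with carry-back sits beside the main result in the forest plot, and its bias was only 0.03 to 0.08 in the Step 4 scenario. Observed Cases by component can retain the affected patients' other items. The SAP calls the study exploratory and proof of concept.

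The points on size stand: the effect is conditional and small when few items are missing, and the understated standard error is the minor part. They do not rescue the rule. Observed Cases for the total drops exactly the affected patients. LOCF can also fill Week 12 differently, so a gap between it and the main result cannot be traced to the baseline rule. An exploratory label does not excuse a main estimate that ignores recorded scores, particularly as SAP 7.1 intends the interim results to inform future trials.

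**Conclusion.** The concern holds. The main analysis sets a missing Week 1 item to 3 unconditionally, the resulting shift can go in either direction, and the pooled variance carries nothing for it. The shift in the mean matters more than the standard error.

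The size cannot be fixed from the documents. It is zero if no Week 1 item is missing or if the missing items average 3, and trivial for one patient. With two items in three patients it is about 0.4 point, with little effect on the false-positive rate but a possible loss of power when the true effect is modest. With eight patients it is about 1 point and the test is no longer reliable at SD 3. These figures rest on assumed item means, spread, correlation and missingness. The reading of the rule and the per-item arithmetic need no such assumptions. The wording should be corrected before the analysis is run.

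**What to change.** In SAP 9.2.1, delete the sentence that assigns 3 to baseline values under multiple imputation, and replace it with a rule along these lines:

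- A Week 1 item that is missing but scored later is imputed within the multiple-imputation model from its next scored visit, by the FCS discriminant option already in 8.4, so that draws stay within 1 to 5.
- If that model cannot be fitted, the next scored value is carried back.
- The score is 3 only if the item is never scored for that patient, as in the LOCF rule.

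Leave the Week 12 imputation as in 8.4. State in 8.8 that 9.2.1 governs BWAT because there is no Screening score.

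Name the predictor explicitly. With all six later weeks as predictors, the discriminant covariance was singular in 15% of runs with 3 patients affected and in essentially all runs with 8. With the next visit alone, it was singular in 0.3% of runs with 3 patients and about 4% to 7% with 8. Rounded normal draws from all six later weeks left a bias of 0.31 to 0.35 point with 8 patients, so they are the weaker choice.

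The cost is SAP wording and programming; no new data are needed. Intervals become wider than with complete data: mean width 3.36 against 3.24 with 3 patients (about 4%), and 3.52 against 3.22 with 8 (about 9%). The draw can only take values seen at Week 1 in other patients. If 8 patients lack the items, mainly those with worse scores, a bias of 0.16 to 0.20 point remains, against 0.71 to 1.19 with the constant. Items never scored are not improved.

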9.2.2 Secondary endpoints

9.2.2.1 *Change from baseline in BWAT total and component scores by visit*

BWAT Score is collected at Week 1, Week 2, Week 4, Week 6, Week 8, Week 10, Week 12 and Follow-up. Differences in absolute and relative change from baseline will be also presented. Differences from baseline will be tested using a Paired Student's T-Test. (Shell T-7). Additionally, a figure presenting the evolution (mean, and 95% confidence interval) of the total score and

individual items by visit will be presented (Shell F-2). This analysis will be done using Observed Cases.

9.2.2.2 *The previous analysis will also be done for the secondary and tertiary lesions if there is enough data. Change from baseline in imaging score by visit*

Image evaluation will be summarized separately for the blinded and unblinded reviews. Percentages for each category and their exact 95% confidence interval (Clopper-Pearson) will be presented. Imputation methods will not be used for this score.

9.2.2.3 *Change from baseline in the Pain Visual Analog Scale (VAS) by visit*

Absolute change from baseline will be calculated as differences in the total score from Week 1 to Week 12. Descriptive statistics will be presented. Differences between the two visits will be analyzed using a Paired Student's T-Test. (Shell T-7)

The Week 1 to Week 12 analysis will be done using Multiple Imputation, and supported by the different sensitivity analysis as specified in Section 8.4. A forest plot summarizing these results will be produced presenting the estimated change from baseline and 95% confidence interval for the different imputation methods. These analysis will also be done for the PP population.

Additionally, the VAS Score is collected at Screening, Week 1, Week 2, Week 4, Week 6, Week 8, Week 10, Week 12 and Follow-up. VAS scores will be summarized by visit. Differences in absolute and relative change from Week 1 to each visit will be presented descriptively. Finally, differences in absolute change from Week 12 to Follow-up will be summarized. Statistically significant differences from the reference values will be tested using a Paired Student's T-Test (Shell T-7). Additionally, a figure presenting the evolution (mean, and 95% confidence interval) of the VAS score by visit will be presented (Shell F-2). This analysis will be done using Observed Cases.

9.2.2.4 *Change from baseline in total and subscales of wound QoL score by visit*

Missing values (e.g., missing visits, visits with more than 25% of the items missing, or subscales with more than one item missing) will be imputed. Missing imputation will be done on a subscale level. Absolute change from Week 1 to Week 12 will be done using Multiple Imputation, by each subscale and global score and supported by the different sensitivity analysis as specified in Section 8.4. A forest plot summarizing these results will be produced presenting the estimated change from baseline and 95% confidence interval for the different imputation methods (Shell F-1).

Wound Quality of Life was collected at Week 1, Week 6 and Week 12. Differences in percent and absolute change from Week 1 to each visit by each subscale and in the global score will be analyzed using a Paired Student's T-Test (Shell T-7). Means and 95% confidence interval will be presented graphically by visit for the global score and subscales (Shell F-2). This analysis will be done using Observed Cases.

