### 5.3. Inclusion Criteria

Patients who meet the following criteria will be considered eligible to participate in the clinical trial:

1. Patients with either newly diagnosed CUA OR recurrent CUA that has been dormant with no skin lesion involvement for at least 90 days from study start (new or recurrent diagnosis must be made within 5 weeks of study start)
2. Patients who signed the written informed consent to participate in this clinical trial (prior to any clinical trial-related procedures being performed), after reading the Patient Information Sheet and Informed Consent Form (ICF), and who had the opportunity to discuss the clinical trial with the Investigator or designee
3. Males or females aged  $\geq 18$
4. Patients on maintenance haemodialysis
5. Patients with at least a minimum level of pain on VAS scale or on pain-killers stronger than NSAIDs

6. Females of child-bearing potential should use a highly effective contraceptive measure throughout the study AND have a negative serum pregnancy test at entry. Male patients having sexual relationship in which pregnancy can occur should take adequate contraceptive precautions (wear a condom) (see Section 8.3.1.)

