6.6.4 Wound Quality of Life (Wound-QoL)

The Wound-QoL measures the disease-specific, health-related quality of life of subjects with chronic wounds. It consists of 17 items on impairments which are always assessed in retrospect to the preceding seven days. Answers to each item are coded with numbers (0='not at all' to 4='very much').

A Wound-QoL global score on overall disease-specific quality of life is computed by averaging all items. A global score can only be computed if at least 75% of the items have been answered (i.e., at least 13 in 17 items are valid). Otherwise, the global score will be considered missing.

In addition, subscales of the Wound-QoL can be calculated representing different dimensions of disease specific quality of life by averaging the respective items. A subscale can only be computed if no more than 1 item of the subscale is missing.

The items are assigned to subscales as follows:

- Subscale 'Body': Items #1 to #5
- Subscale 'Psyche': Items #6 to #10
- Subscale 'Everyday life': Items #11 to #16

Item #17 does not belong to any of the subscales.

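### SAP 9.2.2.4 t-tests individual percent change in Wound-QoL, a 0-4 score with 0 as best: a biased and less powerful supplement to the absolute-change endpoint in SAP 5.2.2

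*SAP*

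**What the plan says.** SAP 6.6.4 describes the instrument: "It consists of 17 items on impairments which are always assessed in retrospect to the preceding seven days". The scoring is numeric: "Answers to each item are coded with numbers", from 0 for no impairment to 4 for the strongest degree. The global score averages all items and each subscale averages its own, so every score runs from 0 to 4 and lower is better.

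SAP 5.2.2 lists the Wound-QoL endpoint as absolute change at Weeks 6 and 12 in the global score and subscales. SAP 9.2.2.4 has two analyses:

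- The multiple-imputation analysis from Week 1 to Week 12, with its sensitivity analyses and forest plot, uses absolute change only.
- The by-visit analysis adds percent change: "Differences in percent and absolute change from Week 1 to each visit by each subscale and in the global score will be analyzed using" one named method, the paired t-test. On missing data it says: "This analysis will be done using Observed Cases".

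SAP 9.2.2.4 does not say what happens to the percentage when the Week 1 score is 0. SAP 9.7.2 does have a not-available category for a Week 1 VAS of 0. For relative VAS change by visit, SAP 9.2.2.3 says: "Differences in absolute and relative change from Week 1 to each visit will be presented descriptively".

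**The concern.** Individual percent change suits a 0-4 impairment score poorly, for three reasons.

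1. A Week 1 score of 0 makes the percentage undefined. Under observed cases that patient, who can only stay the same or worsen, leaves the percent test but stays in the absolute test. The two tests then describe different patients.
2. Improvement cannot exceed -100%, while worsening from a low baseline has no comparable limit. The mean of the percentages is therefore pulled upward.
3. The patients with the least impairment carry the most weight. In a trial of 15, one of them can set the sign of the mean.

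Three subscales and a global score at two post-baseline visits give 4 x 2 = 8 percent-change tests. SAP 8.7 makes no multiplicity adjustment. At stake is a supplementary table that may understate an improvement or suggest worsening beside an absolute analysis that shows neither.

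**Working it through.** **Inputs.** From the documents: scores 0 to 4 with 0 best (SAP 6.6.4), a paired t-test on observed cases (SAP 9.2.2.4), and 15 patients (SAP 6.4). The documents give no Wound-QoL mean, SD or correlation between visits, so those below are assumptions shown over a range. The plan states no Wound-QoL figure that could be reproduced first. Its sample size concerns a healing proportion.

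**Formula.** With Week 1 score X and later score Y, percent change is 100(Y - X)/X, defined only for X > 0. The t-test asks whether its mean is 0.

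**Why the mean is pulled upward.** Suppose two patients swap scores a and b. Their mean absolute change is 0. Their mean percent change is 100 x (a - b)^2 / (2ab), which is never negative. With a = 0.4 and b = 2.0:
- the changes are +400% and -80%, with mean (400 - 80)/2 = +160%;
- the formula agrees: 100 x 1.6^2 / (2 x 0.8) = 100 x 2.56/1.6 = 160.

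**One patient can decide the sign.** In a constructed set of 15 patients with identical Week 1 and Week 12 distributions, the mean absolute change is 0.00. One patient starts at 0 and drops out of the percentages. The other 14 average +26.3% (p = 0.44). Without the patient who goes from 0.2 to 1.0 (+400%), the remaining 13 average (14 x 26.254 - 400)/13 = -2.5%.

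**Simulation.** For each scenario, 20,000 trials of 15 patients were drawn from a bivariate normal with SD 0.9, limited to 0-4 and rounded to 0.2, the step of a five-item mean. Patients with X = 0 were excluded from the percent test only.

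No mean change:

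| Assumed baseline mean | Patients at 0 | Mean percent change, correlation 0.5 | Mean percent change, correlation 0.8 |
|---|---|---|---|
| 2.5 | 0.4% | +11% | +5% |
| 2.0 | 1.7% | +17% | +7% |
| 1.5 | 6% | +22% to +23% | +10% |

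The mean absolute change was 0.00 throughout. At correlation 0.5 the percent test rejected toward improvement in about 1% to 2% of trials, below the nominal 2.5%, and its total error was about 4% to 5%. The share at 0 corresponds to 15 x 0.004 = 0.06 up to 15 x 0.06 = 0.9 patients per trial.

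Improvement of 0.5 point (before limiting to the scale):

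| Correlation | Power, percent change | Power, absolute change |
|---|---|---|
| 0.5 | about 31-33% | about 50-51% |
| 0.8 | about 69-72% | about 85-87% |

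**Edges of the range.** A separate item-level simulation varied mean, SD and correlation more widely:
- At a high baseline (mean about 2.9), the bias was only +1% to +11%.
- With 30-36% of patients at 0 on a five-item subscale, the mean percentage was still positive (+5% to +16%), but the t-test rejected toward improvement in 7-9% of no-change trials and toward worsening in under 1%. Excluding the patients who can only worsen causes this reversal.

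**The case against.** The plan already puts absolute change first. It is the defined endpoint, the multiple-imputation analysis uses it, and it is also tested by visit. The percent test is a supplement to a secondary endpoint in an exploratory trial, and no decision rule uses it. All of this stands and limits the point to a minor one. It does not justify keeping a test that serves no stated endpoint. The general Wilcoxon option in SAP 8.1 does not help, because 9.2.2.4 names the t-test.

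The sizes rest on assumed baselines. Eligibility asks for "Patients with at least a minimum level of pain on VAS scale or on pain-killers stronger than NSAIDs", which makes a large share at 0 less likely, but it sets no minimum Wound-QoL score.

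Three stronger readings are tempting, and the material does not support them.

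- **The two tests would contradict each other.** With no mean change and correlation 0.5, the mean percentage is positive while the absolute mean improves in 24-27% of trials, but there the sign of the absolute mean is itself noise. A significant absolute improvement beside a positive mean percentage occurs in under 0.1% of trials with no mean change, and in at most about 1.4% with a 0.5-point improvement. No trial had both tests significant in opposite directions.
- **The mean shows worsening even if nothing moves.** If no patient's score changes, every defined percentage is 0. The bias needs visit-to-visit variation around an unchanged mean.
- **VAS has the same faulty test.** SAP 9.2.2.3 describes relative VAS change as descriptive. Its later t-test sentence does not name percent change, so a power loss for a VAS percent test is not a clear consequence of this plan.

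**Conclusion.** The point holds as a minor fault in a supplementary secondary analysis. SAP 9.2.2.4 tests a quantity outside the endpoint in SAP 5.2.2. Under no mean change that quantity has a positive expected value, about +5% to +23% for assumed baseline means of 1.5 to 2.5, SD 0.9, correlation 0.5 to 0.8 and 15 patients. The bias is smaller at high baselines.

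For an assumed 0.5-point improvement, the percent test gives up about 15 to 20 percentage points of power against the absolute test. In these scenarios the cost is bias and lost power, and false positives are not inflated. If many patients score 0 at Week 1, rejections can instead tilt toward improvement, so the direction of the error cannot be known in advance. The lead analysis of absolute change is not affected.

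**What to change.** In SAP 9.2.2.4, test absolute change only, in line with 5.2.2, and delete the t-tests on percent change. If a percentage is wanted, show it without a test, in one of two forms:

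- mean change divided by mean baseline, over all patients with both visits; or
- the median individual percentage, with the number of patients at a Week 1 score of 0 stated.

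In 9.2.2.3, keep relative VAS change untested and make the t-test sentence refer to absolute change.

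The cost is a few words in the SAP and eight fewer tests. No new data are needed, and no patient with both visits is lost from the tested analysis. The one downside is that individual relative changes are no longer tested. They can still be listed.
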